Due to resourcing constraints faced by the Local Authorities and difficulties providing data to us, we consulted with them to determine for which data fields it would be feasible for them to provide data, we decided to include a reduced set of matching variables than originally planned. This decision was made after consultation with WWCS and after we distributed a survey to Local Authorities, asking about whether particular variables exist in information they have direct access to. A revised list of the matching variables is now reported in Table 3. Originally intended matching variables' table can be found in Appendix C. In response to changes made to matching variables, we also updated the identification strategy and model specification, depending on the level of outcome measures. Since not all Local Authorities that operate FDAC sites agree to provide non-FDAC data (as shown in Table 1), we will use multilevel models to deal with the hierarchical structure.

In addition to the analysis of binary indicator of the use of expert witness, we will include the total number of *different* types of expert witness as an additional outcome to explore the impact of FDAC on the likelihood of expert witnesses being consulted (RQ5).

The final report will include a section on lessons learned, e.g., concerning the reasons for changes made above, such as the availability of data and resources to code this data in Local Authorities.

Intervention and Theory of Change

This section outlines how the intervention is delivered and the Theory of Change (ToC) that was developed with stakeholders during the feasibility stage of this evaluation. Although there is variation in the elements included in FDACs and how they are implemented, the ToC is designed to outline the overarching logic common to the FDAC approach in general. The FDAC logic model and ToC are detailed in Appendices A and B respectively.

Intervention

FDAC provides support to parents to help them overcome their problems to give children the best possible chance of being raised by their own parents. FDAC recognises that very few parents intend to abuse or neglect their children, but that parents fail when they have significant problems. This includes substance and alcohol misuse, domestic abuse, mental health problems and severe poverty.

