FDAC is designed to be a 'problem solving' court that adopts a less adversarial approach than typical care-proceedings. It follows the principle of therapeutic jurisprudence, empowering families with a stronger voice in care proceedings.

How is the intervention delivered?

Each FDAC site has a dedicated FDAC judge. The FDAC judge has jurisdiction over both care-proceedings and the FDAC treatment intervention. The FDAC judge oversees fortnightly reviewing hearings with the multidisciplinary team. Lawyers do not attend the fortnightly review hearings. The multidisciplinary team provides treatment and support to parents, monitoring their progress and reporting back to the court at the fortnightly review hearings. These hearings aim to solve the problems faced by the parent through an open therapeutic forum.

The staffing of the multidisciplinary team varies across FDAC sites, though the core structure includes substance misuse specialists, social workers and an overall site manager.

When and where is the intervention delivered?

The intervention is delivered during care-proceedings, which typically last up to 26-weeks. In some circumstances, extensions to care-proceedings are granted.

There are fourteen FDAC sites, operating within Local Authorities. A full list of FDAC sites and the Local Authorities each site covers is detailed in Table 1, along with 12 Local Authorities who agreed to provide non-FDAC data as part of this evaluation.¹

Table 1 FDAC sites and Local Authorities	
FDAC site	Local Authority
Pan-Bedfordshire	Central Bedfordshire*
	Luton
	Bedford
Birmingham and Solihull	Birmingham City*
	Solihull*
Coventry	Coventry*
	Warwickshire*
East Sussex	East Sussex
Gloucestershire	Gloucestershire
Kent	Kent*
Leeds	Leeds City Council*
London	Bromley
	Camden
	Croydon
	Kingston
	Lambeth
	Merton
	Redbridge*
	Richmond
	Sutton
	Wandsworth
Milton Keynes and Buckinghamshire	Milton Keynes
	Buckinghamshire
Newcastle, Gateshead & North Tyneside	Newcastle
	Gateshead
	North Tyneside
Somerset	Somerset
Southampton	Southampton City Council*

¹ Only one Local Authority who does not operate an FDAC site agreed to provide data.

Stockport	Stockport*
Walsall, Sandwell and Dudley	Sandwell
	Dudley
	Walsall*
Not operating FDAC site	Manchester*

* indicates the 12 Local Authorities that have agreed to provide data as part of this evaluation.

Variation and iterations

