Although the core FDAC model is the same, there are some differences in the implementation of the intervention across sites. For example, some sites have started providing support in pre-proceedings (London and Kent) or post-proceedings (Gloucestershire). Some sites also use peer-mentoring, where successful parents support parents in care-proceedings. This study focuses on the overall effectiveness of FDAC across sites.

Separate evaluations are being conducted on behalf of the What Works Centre for Social Care which will explore these variations in greater detail:

- Peer-mentoring; evaluated by King's College London.
- Post-proceedings support in the Gloucestershire FDAC; evaluated by the University of Sussex.
- Engagement with FDAC using behavioural insights; evaluated by the Centre for Evidence Implementation.

Impact Evaluation

Research questions

The impact evaluation will seek to answer the following questions:

RQ1 What is the impact of FDAC on the likelihood that children are reunited with their parents at the end of care proceedings relative to non-FDAC care proceedings as usual?

RQ2 What is the impact of FDAC on the likelihood that parents continue to misuse alcohol or drugs by the end of care proceedings relative to non-FDAC care proceedings as usual?

RQ3 What proportion of children reunified at the end of FDAC care proceedings are still placed with their parent(s) three years after final court hearing and how does this compare with the national average?

RQ4 What is the impact of FDAC on the likelihood of final care proceedings hearings being contested relative to non-FDAC care proceedings as usual?

RQ5 What is the impact of FDAC on the likelihood of external expert witnesses being consulted during care-proceedings relative to non-FDAC care proceedings as usual?

RQ6 What is the impact of FDAC on the placement of the child at the end of care proceedings relative to non-FDAC care proceedings as usual?

Participants

Study participants will be drawn from 14 FDAC sites (for the intervention group) and from 12 Local Authorities (for the control group). Participants in the intervention group will be those

going through FDAC court proceedings. Control cases will be selected from non-FDAC care proceedings as usual cases.

Eligibility for study inclusion² is defined as the following:

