- **Intervention** – all cases that have been referred to an FDAC that were open between October 2019³ and June 2022 and a final hearing took place by October 2022 will be considered eligible.
- **Control** – any case that meets the basic criteria for an FDAC referral and sits within an area covered by a Local Authority⁴ that has an FDAC but receives non-FDAC care proceedings as usual that were open between October 2019 and June 2022 and a final hearing took place by October 2022 will be considered eligible.

The basic criterion for FDAC referral is that “Parental substance misuse (drugs or alcohol or both) is a key factor of the Local Authority’s concerns about the child(ren) within a care proceedings case”. This will be captured for FDAC cases from a suite of variables, including:

- Current or historical misuse of drugs or alcohol
- Substance misuse type
- Severity of alcohol misuse
- Severity of drug misuse

This data is not systematically collected by Local Authorities for non-FDAC cases. Instead, care proceedings case data is typically recorded in court bundles and case notes. In June 2022, we distributed a survey to Local Authorities to determine which data fields for non-FDAC cases exist in their records, whether Local Authorities have direct access to that information, and whether it would be feasible for them to provide data for those fields. Based on their responses, we adjusted the data collection template and revised the study protocol. Some FDAC sites have developed their own referral inclusion and exclusion criteria though the variation between sites has never been closely documented. For instance, some FDAC sites exclude cases where parental psychosis or litigation capacity may act as a barrier to parental engagement with FDAC or where there is a history of severe physical or sexual abuse of a child. Furthermore, the selection process likely varies by FDAC site in regard to subjective components that are not included within the criteria. There is therefore likely to be a degree of selection bias, with systematic differences between control and treatment participants.

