FDAC case data will be retrieved directly from CJI following the development of a data sharing agreement. This data sharing agreement should be sufficient to enable access to all necessary FDAC data for the purposes of the study. Alternatively, however, separate data sharing agreements may have to be drawn for each of the individual FDAC sites. Further data sharing agreements will also be drawn for each of the participating Local Authorities in order to grant access to the necessary control case data.

Design

Table 2 Study design

² Note that this refers to RQ1, 2, 4 and 5. RQ3 draws on data from a prior cohort of FDAC participants (2017 and 2018).

³ Previously this was January 2021 – we expanded the date range to maximise sample size.

⁴ Manchester was the only Local Authority that agreed to provide non-FDAC care proceeding as usual data without an FDAC site in their area.

Study type and number of arms		Quasi-experimental design: Coarsened Exact Matching
Unit of identification		Case, parent, and child
Matching variables		Parent demographics, Domestic Violence, Alcohol or drug misuse, Child demographics, Case characteristics (see Table 3).
Primary outcome	variable	Reunification
	measure (instrument, scale)	Binary indicator derived from the placement of the child at the end of care proceedings.
Secondary outcomes	variables	
 1) Alcohol and drug misuse cessation; 2) Contested final hearing; and 3) Use of expert witnesses.
	measures (instrument, scale)	
 1) Binary indicator of whether the parent's alcohol and/or drug misuse has ceased; 2) Binary indicator of whether the final hearing was contested; 3) a) Binary indicator of whether expert witnesses were used during care proceedings; and b) Count of the number of different types of expert witness (based on the binary expert reports/assessments indicators, e.g. independent social work assessment, psychiatric assessment).

A randomised controlled trial was considered for this evaluation but was rejected as the judiciary thought that randomisation of families in care-proceedings could be subject to legal challenge. A feasibility study was conducted as part of this evaluation considering suitable evaluations. The impact evaluation, therefore, uses a quasi-experimental design: Coarsened Exact Matching (CEM).

Identification strategy

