Where $P(\text{Reunification}_{ipcs})$ is the probability of reunification. Children (i) are nested within primary carers (p), cases (c), and sites (s). The vector X_{ipcs} denotes the uncoarsened covariates. The random intercepts are represented as u_{pcs} , u_{cs} , u_s , respectively. Should the random intercept adjustments at primary-carer-level and case-level be significantly highly correlated (over .8) with each other, we will drop case-level random intercepts from the model.

The multilevel models described above will be estimated using the *melogit* command in Stata.

Additional Analysis

As a sensitivity analysis, we will fit a multilevel logistic regression model on the matched sample excluding the characteristics used in the matching in the regression model:

$$P(\text{Reunification}_{ipcs}) = \text{logit}^{-1}(\beta_0 + \beta_1 \text{Intervention}_{ipcs} + u_{pcs} + u_{cs} + u_s)$$

Secondly, we will also assess the impact of FDAC on the placement of the child (RQ6), using a categorical outcome variable that indicates 1) reunification with the child’s parents 2) placement with another relative, or 3) LA care. This will be assessed using a multilevel multinomial logistic regression.

$$P(\text{Placement}_{ipcs}) = \text{logit}^{-1}(\beta_0 + \beta_1 \text{Intervention}_{ipcs} + \beta_2 X_{ipcs} + u_{pcs} + u_{cs} + u_s)$$

As with the primary analysis, we include the uncoarsened covariates used in matching. We will present effect sizes as relative risk ratios, with 95% confidence intervals. The risk ratio will be estimated as described above.

Missing data analysis

⁸ Site refers to case locations, as shown in Table 1. Control cases will be coded as the FDAC site that serves their Local Authority (e.g. both Coventry and Warwickshire non-FDAC data will be allocated to Coventry site data). Manchester will be coded independently as there is no FDAC site.

If greater than five percent of cases are missing outcome data on the primary analysis, it is likely that missingness may impact the results of the evaluation and we will therefore consider conducting additional analysis for the primary outcome.

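### Five of 14 FDAC sites have no controls and Manchester has only controls, so the FDAC effect is partly confounded with area, and no planned analysis shows by how much

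*Supplement*

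**What the plan says.** The Participants section gives the two sources: "Study participants will be drawn from 14 FDAC sites (for the intervention group) and from 12 Local Authorities (for the control group"). In Table 1 an asterisk "indicates the 12 Local Authorities that have agreed to provide data as part of this evaluation".

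The section on variations from the original design gives the reason for the modelling choice: "Since not all Local Authorities that operate FDAC sites agree to provide non-FDAC data (as shown in Table 1), we will use multilevel models". The sentence goes on to name the hierarchical data structure as what the models address. In the Primary Analysis the only site term is a random intercept, beside random intercepts for primary carer and case. Footnote 8 defines site: "Control cases will be coded as the FDAC site that serves their Local Authority", and "Manchester will be coded independently as there is no FDAC site".

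Control eligibility covers "any case that meets the basic criteria for an FDAC referral and sits within an area covered by a Local Authority", and the text then requires that the authority has an FDAC. Footnote 4, attached at that point, records the exception: "Manchester was the only Local Authority that agreed to provide non-FDAC care proceeding as usual data without an FDAC site in their area". The note to Table 1 says the same: "Only one Local Authority who does not operate an FDAC site agreed to provide data".

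Table 3 lists no site, Local Authority or region among the matching variables for any outcome. The power section assumes no clustering by Local Authority.

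**The concern.** A child in one of the five sites without controls can be compared only with children from other areas. Manchester's controls can be compared only with FDAC children from elsewhere. If usual reunification rates differ by court or authority, part of the estimated FDAC effect is a difference between places. The documents give some reason to expect such variation: the Contextual Factors section says the effects of COVID-19 varied across sites.

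A random intercept does not supply the missing local comparison. It treats site effects as draws from one distribution that is independent of FDAC status. In a site with one arm, the site effect and the FDAC effect are separated only by that assumption.

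The planned checks would not show the problem. Hedges' g and the L1 statistic cover the matching covariates, and site is not one of them. The sensitivity analyses collapse the coarsening further, drop covariates from the regression, or impute missing outcomes. None isolates the contrast within sites. The Participants section admits bias from how FDAC sites select cases, but does not discuss area.

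**Working it through.** **1. Count from Table 1.** Control authorities per FDAC site:

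| Site | Authorities listed | Supplying controls |
|---|---|---|
| Pan-Bedfordshire | 3 | 1 |
| Birmingham and Solihull | 2 | 2 |
| Coventry | 2 | 2 |
| Kent | 1 | 1 |
| Leeds | 1 | 1 |
| London | 10 | 1 |
| Southampton | 1 | 1 |
| Stockport | 1 | 1 |
| Walsall, Sandwell and Dudley | 3 | 1 |
| East Sussex | 1 | 0 |
| Gloucestershire | 1 | 0 |
| Milton Keynes and Buckinghamshire | 2 | 0 |
| Newcastle, Gateshead & North Tyneside | 3 | 0 |
| Somerset | 1 | 0 |

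That is 11 control authorities in 9 sites, plus Manchester, which makes 12. Five sites have none.

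**2. The plan's own detectable effect.** Inputs from the power section: 430 cases, 1.4 children per case, ICC 0.70, R² 0.20 (level one) and 0.10 (level two), control rate 25%, two-sided 5%, power 80%.

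- MDES = (1.960 + 0.842) × √[0.70 × 0.90 / (0.25 × 430) + 0.30 × 0.80 / (0.25 × 430 × 1.4)] = 2.802 × √(0.00586 + 0.00159) = 0.242
- OR = exp(0.242 × π/√3) = 1.55
- RRR = 1.551 / (0.75 + 0.25 × 1.551) = 1.363, or 9.1 points

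The stated 1.36 and 9.1 points reproduce. This needs the level-two R² on the ICC term and an exponential for the OR. With the R² terms placed as Appendix F prints them, the result is 1.35 and 8.8 points. The calculation sets Local Authority clustering to zero, so it says nothing about area differences.

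**3. How much of an area difference passes through.** Assumptions, not in the documents: 215 cases per arm, FDAC cases equal over 14 sites (15.36 each), controls equal over 10 areas (21.5 each), a linear random-intercept model, no covariates, no matching weights.

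Set residual variance to 1 and τ² = ICC/(1 − ICC). For a site with f FDAC cases and n cases in all, let g = τ²/(1 + nτ²). Sum over sites A₁₁ = n/(1 + nτ²), A₁₂ = f/(1 + nτ²) and A₂₂ = f − g f². With S the part of A₁₁ that comes from the five FDAC-only sites, the share of their baseline difference that enters the FDAC coefficient is S(A₁₁ − A₁₂)/(A₁₁A₂₂ − A₁₂²).

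At ICC 0.05, τ² = 0.0526:

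- nine mixed sites: 112.8, 47.0, 100.2
- five FDAC-only sites: 42.5 in each sum, so S = 42.5
- Manchester: 10.1, 0, 0
- totals: 165.4, 89.5, 142.7
- share = 42.46 × 75.90 / 15,589 = 0.207

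| Site ICC | Five FDAC-only sites | Manchester |
|---|---|---|
| near 0 | 36% | −10% |
| 0.01 | 31% | −9% |
| 0.03 | 25% | −7% |
| 0.05 | 21% | −6% |
| 0.10 | 14% | −4% |

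For an assumed difference of 5 to 10 points in the five sites: 0.141 × 5 = 0.7 to 0.313 × 10 = 3.1 points.

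**4. Simulation on the binary outcome.** There were 600 replicates at case level, with no true FDAC effect, a 25% rate elsewhere, the site variance estimated, and a further site SD of 0 or 0.3 on the logit scale.

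| Rate in the five sites | Spurious effect, random intercept | Type I error |
|---|---|---|
| 25% | −0.1 points | 5–6% |
| 30% | +1.4 to +1.7 points | 6–7% |
| 35% | +2.4 to +3.1 points | 8–10% |

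A stratified estimate from the nine mixed sites stayed at a risk ratio of about 0.99, with type I error of 3 to 6%.

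**5. Precision on nine sites.** Under equal site sizes 215 × 9/14 = 138 FDAC cases remain.

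- If controls shrink equally: MDES = 0.242 × √(430/276.4) = 0.302, RRR 1.46, 11.6 points.
- If 215 controls are kept: RRR 1.42, 10.4 points.
- The FDAC share in the five sites is not given. Over an assumed 10% to 50%, the RRR is 1.38 to 1.53 (controls shrink) or 1.37 to 1.45 (controls kept).

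**The case against.** Several stronger readings are tempting, and the documents do not support them.

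- **That the plan claims random intercepts cure the missing controls.** It does not. The sentence gives the missing authorities as its reason, but names the hierarchical structure as what the models handle, and the analysis section speaks of clustering.
- **That FDAC is wholly confounded with area.** Nine sites hold both arms and give a within-site contrast, so the confounding is partial.
- **That 5/14 = 36% of any area difference, or 3.6 points for a 10 point gap, becomes bias.** That is the unadjusted comparison, which is not planned. The random intercept removes some of it: at ICC 0.10 the share falls from 36% to 14%.
- **That Manchester is a hidden breach of eligibility.** It is disclosed in Table 1 and in footnotes 1, 4 and 8. Its cases were also not passed over by a local FDAC, so they avoid the site-level selection that the plan admits. Removing them from the primary pool would trade one bias for another.
- **That the nine-site estimate is the unbiased answer.** Local controls are cases that did not go to FDAC, so case selection remains. Within-site is not within-authority either: London has controls from 1 of 10 listed authorities, and Pan-Bedfordshire and Walsall/Sandwell/Dudley from 1 of 3 each. The plan's question is effectiveness across all sites, and a difference between the two estimates could be a real difference in effect.

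These points limit the size of the concern and the weight that the remedy can bear. They do not answer the gap: nothing planned shows how far the estimate rests on comparisons between areas.

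**Conclusion.** The concern holds in a limited form. The counts are certain, site is absent from the matching, and the only site term assumes independence from FDAC status. Area differences can therefore enter the primary estimate in part, unseen.

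The size is conditional. The 0.7 to 3.1 points rest on an assumed 5 to 10 point baseline difference, a site ICC between 0.01 and 0.10, and the simplified layout above. Equal site sizes are doubtful, and matching weights would shift the shares. The direction is unknown, so the plan cannot be said to favour FDAC. At the upper end the bias is about a third of the detectable 9.1 points (3.1/9.1 = 34%), enough to colour a borderline result. This calls for a planned sensitivity analysis and a stated limitation, not a new primary analysis.

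**What to change.** Keep the primary analysis as planned and add:

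- A mandatory, pre-specified sensitivity analysis on the nine sites with both arms, re-matched within that subset, with site as fixed effects, reported beside the primary estimate.
- The primary result with and without Manchester.
- A table of cases by site and arm, before and after matching.
- A statement that area confounding limits the primary conclusion, and that a gap between the two estimates may reflect area differences, differing effects across sites, or both.

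No new data are needed, since site is already coded under footnote 8. The cost is a second matching run, extra models and lower precision in the nine-site analysis, as worked out above. That analysis also covers fewer sites and still carries FDAC case selection, so it should be read as a check on the primary estimate and not as its replacement.

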The intervention group will consist of cases that have been selected by an FDAC site to receive FDAC care proceedings. A control group will be selected from non-FDAC cases that meet the basic criteria for inclusion in an FDAC but were not selected for FDAC. The basic criteria for inclusion in FDAC are that care proceedings have been issued and that there are concerns about parental alcohol or drug misuse as part of the care proceedings case. The average treatment effect will be estimated by combining a CEM approach, as described by lacus et al. (2009), with regression analysis.

Implementing CEM requires data for characteristics associated with selection into the intervention or the outcome at the start of care proceedings (see Table 3 for a list of all variables used to implement matching). For example, this could include risks to the child (such as parental alcohol or drug misuse or domestic violence in the household). Variables will be “coarsened” into binary or categorical variables (for example, if it is a continuous variable, such as the age of the child, the variable would be re-categorised into age bands). Some variables that are already collected in FDAC sites are currently collected categorically and will not require coarsening.

However, due to resourcing constraints faced by the Local Authorities, some variables collected ordinarily in FDAC cases will require recoding to be comparable to those in non-FDAC cases. For example, parental alcohol and drug misuse at the start of proceedings are assessed using clinical judgement (high, medium and low risk). Substance misuse is recorded differently by Local Authorities for non-FDAC cases, which only comprise types of parental substance misuse rather than clinical judgement of severity. Therefore, to be comparable to non-FDAC cases, severity of parental alcohol and drug misuse at the start of proceedings in FDAC cases will be recoded as general type of parental substance misuse (i.e. Drugs, Alcohol, Drugs and Alcohol, None, and Unknown). The recoded variable will then not require coarsening. Table 3 outlines the variables collected and how they will be coarsened for matching. A sensitivity analysis will test the impact of further collapsing coarsened variables.

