The matching will be conducted using the user-written package *cem* in Stata 17.1 SE (Blackwell et al., 2010), which implements CEM as described in Iacus et al. (2009). The primary analysis will be conducted on an intention-to-treat basis where the outcome is non-missing. Where covariate data is missing, the *cem* package matches cases that are missing data on the same covariates. If missing outcome data exceeds five percent of the intervention sample, we will consider conducting a sensitivity analysis using multiple imputation (see missing data analysis).

Any intervention cases excluded from the analysis because no match can be found will be transparently reported using a CONSORT flow diagram. If more than five percent of intervention cases are lost because of issues with common support, we will consider adjusting how covariates are coarsened. This would involve collapsing categories of coarsened covariates and altering bin sizes. A summary of matching variables and how they will be coarsened can be found in Table 3.

Analysis

A “doubly robust” estimation of causal effects will be estimated for the matched sample, applying the weights assigned during the matching, including a binary indicator of allocation to FDAC, while also including the uncoarsened matching covariates in the regression model, following Funk et al. (2011). The “doubly robust” estimation reduces the risk that the average treatment effect on the treated (ATT) is biased, provided that either the matching (modelling exposure to the intervention) or the regression model (describing the relationship between the dependent and independent variables) is well specified (Funk et al., 2011). To account for the clustering of children within primary carers, cases and within sites (as shown in Table 1)⁸, we will use a multilevel logistic regression model. The full model is as follows:

$$P(\text{Reunification}_{ipcs}) = \text{logit}^{-1}(\beta_0 + \beta_1 \text{Intervention}_{ipcs} + \beta_2 X_{ipcs} + u_{pcs} + u_{cs} + u_s)$$

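### The intervention arm is defined by referral in one place and by selection or FDAC proceedings in others, so a case referred but not accepted can meet both arm definitions

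*Supplement*

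**What the plan says.** Protocol version 2.0 describes the intervention group in three ways.

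- **Participants, opening paragraph:** those "going through FDAC court proceedings".
- **Participants, eligibility bullet:** "all cases that have been referred to an FDAC", subject to the date window.
- **Identification strategy:** "cases that have been selected by an FDAC site to receive FDAC care proceedings".

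Controls are described in two ways. The eligibility bullet takes "any case that meets the basic criteria for an FDAC referral", within the area of a Local Authority with an FDAC, that has usual proceedings and meets the same date window. The Identification strategy says: "A control group will be selected from non-FDAC cases that meet the basic criteria for inclusion in an FDAC but were not selected for FDAC".

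On the analysis population, the Matching section states: "The primary analysis will be conducted on an intention-to-treat basis where the outcome is non-missing". The Analysis section that follows names the average treatment effect on the treated (ATT) as the quantity to be protected from bias. Neither section names the event that places a case in an arm.

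FDAC data come from the FDAC data collection tool. Control data come from Local Authority systems and case notes. No rule covers a case that appears in both.

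**The concern.** Referral, selection and entry are separate events in this setting. Variation between sites describes sites choosing among cases that already meet the inclusion criteria. Participants adds site-specific criteria and subjective selection. Cases that are referred but not taken on are therefore foreseeable, and the plan does not place them consistently.

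Two things depend on where they go. The first is the estimand: a referred arm estimates the effect of being referred, a selected arm the effect of being taken into FDAC. The first sits badly with the named ATT, because part of the arm was never treated. The second is analyst freedom: with both wordings in the plan, the choice can be made after outcomes are known.

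Matching cannot be relied on to repair a misplacement. The examples of site exclusions under Participants (psychosis, litigation capacity, a history of severe abuse of a child) have no counterpart among the matching variables in the current Table 3.

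**Working it through.** **Step 1: the definitions applied to one case.** Take a case inside the date window, in a participating Local Authority with an FDAC, that is referred, not accepted and then heard in usual proceedings.

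| Rule | Intervention? | Control? |
|---|---|---|
| Participants, opening paragraph | No | Not addressed for this case |
| Participants, eligibility bullets | Yes (referred) | Yes (meets the criterion, has usual proceedings) |
| Identification strategy | No (not selected) | Yes (not selected) |

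The double membership arises within the eligibility bullets alone, from the referral wording. The date conditions are the same for both arms, so they do not separate them.

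**Step 2: where the overlap can occur.** Twelve Local Authorities supply control data. Table 1 shows Manchester as having no FDAC, which leaves 12 − 1 = 11.

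**Step 3: the plan's own effect figure.** Inputs from the minimum detectable effect section: ICC 0.70; R-squared 0.20 (level one) and 0.10 (level two); 430 cases in total; 1.4 children per case; equal arms; two-sided alpha 0.05; power 0.80; control rate 25%. With about 400 degrees of freedom the multiplier is about 2.81. Pairing the ICC with the level-two R-squared:

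- MDES = 2.81 × √[0.70 × 0.90 / (0.25 × 430) + 0.30 × 0.80 / (0.25 × 430 × 1.4)] ≈ 0.2425
- OR = exp(0.2425 × π/√3) = 1.552
- RRR = 1.552 / (0.75 + 0.25 × 1.552) = 1.364
- Difference = 25 × 0.364 = 9.1 points

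This reproduces the stated 1.36 and 9.1 points. (The R-squared terms as printed in Appendix F give 1.352 and 8.8 points. That does not bear on this point.) The stated figure is unaffected by the arm definition. It serves only as the effect to dilute.

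**Step 4: dilution under the referral rule, for illustration.** Let f be the share of the referred arm never accepted. The documents do not give f, so it is varied. Assume these families reunify at the 25% control rate. The expected difference is then (1 − f) × 9.1.

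| f | Difference (points) |
|---|---|
| 0% | 9.1 |
| 10% | 8.2 |
| 20% | 7.3 |
| 30% | 6.4 |
| 40% | 5.5 |

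The result also depends on the assumed rate. At f = 20% with a 15% rate, the arm reunifies at 0.8 × 34.1 + 0.2 × 15 = 30.3%, a difference of 5.3 points instead of 7.3. The documents support neither rate for these families.

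**The case against.** The best defence is that the definitions can be read together. The eligibility bullet may describe a screening pool, which the opening paragraph and the Identification strategy then narrow. On that reading the proceedings a case receives fix its arm, as RQ1 implies, and a refused case is a control. This is reasonable and probably what was meant, but the plan does not say so, and the eligibility bullet contradicts it. The objection narrows the point to one wording. It does not remove it.

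Three stronger inferences are tempting, and the documents do not support them.

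- **That refused families among the controls bias the result in favour of FDAC.** This assumes refusals mark poor prognosis. Contextual Factors Analysis says existing sites were unable to take new cases during COVID-19, so some refusals may reflect capacity, and those families could be good comparators. The site exclusions are also described as referral criteria, so some families may never be referred. The plan already discloses selection bias in general terms.
- **That the same families are in fact supplied twice.** Nothing shows that the FDAC data hold referrals that were turned down. Overlap is possible only in the 11 Local Authorities above, out of the 32 FDAC-area authorities in Table 1.
- **That the arm should start when parents sign up.** No study definition uses sign-up. The logic model in Appendix A lists assessment and the report to the second hearing before it. Starting there could select FDAC families on early engagement, with no matching filter among controls.

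**Conclusion.** The inconsistency is real and in the current text. The eligibility wording conflicts with the Identification strategy and with the opening of Participants, gives one kind of case two arms, and is left unresolved by the intention-to-treat statement. This is more than missing detail: applied as written, the bullet puts untreated cases into the FDAC arm, against the named ATT.

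The size is unknown. The range of 8.2 to 5.5 points rests on an assumed 10% to 40% never accepted, a 25% reunification rate in those families, and a true effect equal to the plan's 9.1 points. It shows what the referral rule could cost and does not estimate what happened. No direction of bias is established for placing refused cases among the controls, and duplicate records are a possibility to check, not a finding.

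**What to change.** 1. In the eligibility bullet, replace the referral wording with the Identification strategy rule: selected by an FDAC site to receive FDAC proceedings, and kept in that arm even if the family later exits. Bring the opening paragraph of Participants into line.
2. Define controls in both sections as eligible cases not selected.
3. State in the Analysis plan that intention-to-treat and the ATT both refer to the selection event.
4. Before matching, check for cases supplied by both the FDAC and Local Authority sources, remove the duplicates, and report the counts in the flow diagram.
5. Where referral outcome is already recorded, flag referred-but-not-selected cases and run a sensitivity analysis that excludes them from the controls.

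The cost is a wording change, a record check and possibly slightly fewer cases. Item 5 is limited to existing records because the plan reports resource constraints in the Local Authorities, and no document shows that referral outcomes are held or can be linked.
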